7.7.4. Disease Control Rate

Disease control rate (DCR) is defined as proportion of subjects who have a confirmed response (CR or PR) or SD without PD within 81 days (12 weeks – 3 days) at study start, or durable SD following PD. In the alternative analysis, used for sensitivity analysis in parallel with alternative algorithm for BOR, described previously it is defined as proportion of subjects who have a confirmed response (CR or PR) or SD without PD within 81 days at study start.

DCR and number of subjects with disease control will be tabulated using IERC and investigator assessments.

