	
 
• To assess duration of response (DOR), disease control rate (DCR), duration of stable disease (SD), time to response, and progression-free survival (PFS) time per RECIST 1.1
 
	
 
• DOR per RECIST 1.1, as determined by an IERC and investigator, defined as time from first observation of response to first observation of documented disease progression (or death within 12 weeks after last tumor assessment). Subjects without an event at analysis cutoff date will be censored on date of last tumor assessment.
 
• DCR, defined as proportion of subjects with complete response (CR), partial response (PR), or stable disease (SD) for at least 12 weeks
 
• Duration of SD, measured from the start of treatment until the criteria for progression are met, taking as reference the smallest measurements recorded since the treatment started, including baseline measurements.
 
• Time to response, defined as the time from the first dose date to first observation of confirmed response.
 

	Objective	Endpoint
Secondary (continued)		
 
PFS time, defined as time from first treatment administration to first observation of documented disease progression (or death within 12 weeks after last tumor assessment), per RECIST 1.1, as determined by an IERC and investigator. Subjects without an event at analysis cutoff date will be censored on date of last tumor assessment.
 

	
 
To assess overall survival (OS) rate
 
	
 
Median OS and OS rate
 

	
 
To assess OS time
 
	
 
OS time, defined as time from start of treatment to death. For subjects who are still alive at time of data cutoff for trial analysis or who are lost to follow-up, survival will be censored at the last recorded date that the subject is known to be alive as of the cutoff date for analysis
 

Exploratory		
	
 
To explore the association of programmed cell death protein 1 – ligand 1 (PD-L1) expression with clinical outcomes
 
	
 
Baseline expression of PD-L1 association with clinical outcomes
 

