#### **8.3.3.1. Efficacy Parameters**

Efficacy parameters, including confirmed ORR according to RECIST 1.1, as determined by investigator; disease control rate (DCR), defined as proportion of subjects with CR, PR, or SD for at least 12 weeks; duration of response (DOR) according to RECIST 1.1; time to response (TTR); and duration of stable disease, defined as time from treatment start until documented

progression, will be listed and summarized in Phase 2 using both IERC and investigator assessments.

DOOR and TTR will be summarized in only a subset of patients with confirmed response using the Kaplan-Meier method and displayed graphically, where appropriate. The median event time and 95% CI for the median will be provided. Duration of stable disease will also be summarized by the Kaplan-Meier method.

In addition, PFS, and OS time will be presented in subject listings, analyzed using Kaplan-Meier method and displayed graphically where appropriate. The median event time and 95% CI for the median will be provided.

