- Anti-drug antibody (ADA) concentrations and correlation with AGEN2034 PK exposure metrics
- Confirmed ORR per RECIST 1.1, as determined by an investigator
- DOR per RECIST 1.1, as determined by an IERC and investigator, defined as time from first observation of response to first observation of documented disease progression (or death within 12 weeks after last tumor assessment). Subjects without an event at analysis cutoff date will be censored on date of last tumor assessment.
- DCR, defined as proportion of subjects with complete response (CR), partial response (PR), or stable disease (SD) for at least 12 weeks
- Tumor control rate (TCR), defined as proportion of subjects with CR, PR, or SD lasting at least 6 weeks

Note: endpoint not originally in the protocol, added in SAP

- Time to response, defined as the time from the first dose date to first observation of confirmed response.
- PFS time, defined as time from first treatment administration to first observation of documented disease progression (or death within 12 weeks after last tumor assessment), per RECIST 1.1, as determined by an IERC and investigator. Subjects without an event at analysis cutoff date will be censored on date of last tumor assessment.
- Median OS and OS rate
- OS time, defined as time from start of treatment to death. For subjects who are still alive at time of data cutoff for trial analysis or who are lost to follow-up, survival will be censored at the last recorded date that the subject is known to be alive as of the cutoff date for analysis.

3.6. EXPLORATORY ENDPOINTS OF PHASE 2

- [REDACTED]
- [REDACTED]
- [REDACTED]

Note: The analysis of exploratory endpoints is not covered in this SAP. If applicable, these analyses will be performed according to a separate Exploratory Statistical Analysis Plan.

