7.7. EFFICACY ANALYSIS

7.7.1. Best Overall Response and Objective Response per RECIST 1.1

Best overall response (BOR) will be derived from time-point RECIST 1.1 assessments, either by IERC or by investigator. For the primary endpoint, tumor responses will be evaluated using IERC assessments. In the primary analysis, BOR will be evaluated over all on-study time-point assessments recorded before start of a new anti-cancer therapy, in consideration of RECIST 1.1 definition: “The best overall response is the best response recorded from the start of the study treatment until the end of treatment taking into account any requirement for confirmation. On occasion a response may not be documented until after the end of therapy so protocols should be clear if post-treatment assessments are to be considered in determination of best overall response” (Eisenhauer *et al 2009*). Since all assessments are considered for BOR, the confirmed objective response or stable disease (SD) may occur after a transient time-point progressive disease (PD) assessment(s).

In the secondary analysis, conducted for sensitivity evaluation, an alternative, more conservative approach will be used, evaluating BOR only over time-point assessments until first observed PD, as initially proposed in RECIST 1.0 (Therasse *et al 2000*). Such a definition was implemented in the Charter of IERC, therefore BOR evaluation derived by IERC will be used as sensitivity analysis.

Confirmation of objective response (complete response [CR] or partial response [PR]) is required for respective BOR of CR or PR. Confirmation must be obtained at a subsequent assessment at least 4 weeks apart. In case of CR, the confirmatory assessment must be performed at a consecutive assessment, except for intercurrent non-evaluable assessments.

In case of PR, confirmatory assessment after initial CR/PR may be obtained a) in the primary analysis any time at least 4 weeks apart from the initial assessment, without restrictions on intercurrent assessment b) in the IERC-derived BOR evaluation, any time after 4 weeks and after at most 1 intercurrent assessment of non-evaluable (NE) or SD.

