For patients who did not fulfill requirements for BOR of CR or PR as described above, BOR of SD is defined, in the primary analysis, as i) initial time point assessment(s) of SD, PR, CR without PD at a minimum interval of 39 days (6 weeks-3 days), disregarding NE assessments and/or ii) unconfirmed PR or CR any time at initial evaluation, without PD at a minimum interval of 39 days and/or iii) durable SD following transient PD: at least 2 assessment(s) of SD, PR, CR (ignoring intercurrent NE assessments) at least 39 days (6 weeks-3 days) apart and without new PD within 84 days, counting time from the last transient PD assessment. Subjects who have a response of PR or CR with no subsequent tumor assessments will be assigned a BOR of SD and will be flagged in listings. In the sensitivity analysis performed using IERC-derived BOR evaluation of SD is only considered based on only criterion i) above.

For patients with time point assessment(s) of PD, excluding any transient PDs (PD followed by confirmed objective response or durable SD) and who do not satisfy criteria for BOR of CR, PR, and SD described above, the BOR assessments in the primary analysis will be PD. In the

sensitivity analysis, using IERC-derived BOR evaluation, a similar definition will be used but without excluding transient PDs.

Finally, BOR of NE will be assigned where there are either no evaluable time point assessments at all or first time point assessment(s) of SD was before minimum interval of 39 days without evaluable assessments preformed after 39 days.

The objective response rate (ORR) is the percentage of subjects with a BOR of PR or CR (i.e., objective response). The primary analysis of ORR will include only confirmed responses, with sensitivity analyses based on unconfirmed responses, derived from timepoint assessments according to RECIST 1.1 guidance for studies not requiring confirmation of response (i.e., occurrence of time-point assessment of CR or PR anytime on study). Subjects with missing tumor response status assessment will be counted as non-response (that is, subjects without any follow-up assessment) will be counted in the denominator for ORR.

BOR determined by investigator and by IERC will be compared by cross-tabulating categories of both BOR evaluations in a 2-way table.

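### SAP 7.7.4 counts SD as disease control if no PD is recorded within 81 days, so a week-6 SD scan followed by death, new therapy or no further evaluable scan qualifies, against the 12 weeks of SD required in SAP 3.5

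*SAP*

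**What the plan says.** Protocol 8.3.3.1 gives "disease control rate (DCR), defined as proportion of subjects with CR, PR, or SD for at least 12 weeks", and SAP 3.5 repeats it: "DCR, defined as proportion of subjects with complete response (CR), partial response (PR), or stable disease (SD) for at least 12 weeks". Protocol 2.1.2 describes how SD is timed: "Duration of SD, measured from the start of treatment until the criteria for progression are met".

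The derivation in SAP 7.7.4 is the "proportion of subjects who have a confirmed response (CR or PR) or SD without PD within 81 days", where 81 days is explained as 12 weeks less 3 days. The primary version adds durable SD following PD. The alternative version drops that limb but keeps the 81-day wording.

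SAP 7.7.4 has no definition of SD of its own, so the BOR rules in SAP 7.7.1 apply. The first criterion for SD there is "initial time point assessment(s) of SD, PR, CR without PD at a minimum interval of 39 days", with non-evaluable (NE) scans disregarded. SAP 7.7.1 adds: "Subjects who have a response of PR or CR with no subsequent tumor assessments will be assigned a BOR of SD". Missing follow-up leads to a BOR of NE only if there is no evaluable scan at all, or if the "first time point assessment(s) of SD was before minimum interval of 39 days without evaluable assessments preformed after 39 days".

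SAP 3.5 and 7.7.5 also define TCR, in which SD needs to last only 6 weeks. SAP 5.10 refers missing efficacy assessments to Section 7.7.

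**The concern.** For subjects scanned through week 12, absence of PD within 81 days is a fair way to implement 12 weeks of SD, and it agrees with how the protocol times SD. The difficulty is with SD subjects who are not scanned that far. The derivation treats lack of a recorded PD as evidence of control, whether or not anyone looked.

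Such subjects are foreseeable. Protocol 4.4.1 provides for withdrawal on clinical progression without radiologic PD. Protocol 6.4.4.1 runs Phase 2 imaging only until study drug is discontinued, although Table 13 footnote 7 continues it until centrally determined PD. Whichever imaging rule is followed, there are no scans after death.

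At stake is a secondary endpoint tabulated for both the IERC and the investigator and broken down by subgroup. Two programmers, one working from SAP 3.5 and one from 7.7.4, could report different DCRs from the same data.

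**Working it through.** **Thresholds.** 12 × 7 − 3 = 81 days and 6 × 7 − 3 = 39 days; both SAP figures reproduce. Scans are every 6 weeks ± 3 days, so by simple difference the week-6 window is 42 ± 3 = days 39 to 45 and the week-12 window is 84 ± 3 = days 81 to 87.

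**Applying the rule.** The 81-day limb as written needs BOR of SD under SAP 7.7.1 (one SD, PR or CR scan at day 39 or later, NE ignored) and no PD by day 81. The last column adds an evaluable assessment at the week-12 visit or later, with no death or new therapy before it.

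| History | As written | With week-12 assessment required |
|---|---|---|
| SD day 42, death day 60 | controlled | not controlled |
| SD day 42, new therapy day 50, no PD recorded by day 81 | controlled | not controlled |
| SD day 42, no further scan | controlled | not controlled |
| SD day 42, NE day 84 | controlled | not controlled |
| Unconfirmed PR day 42, no further scan | controlled | not controlled |
| SD day 42, PD day 80 | not controlled | not controlled |
| SD day 42, PD day 84 | controlled | controlled |
| SD days 42 and 84 | controlled | controlled |

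Every change runs from controlled to not controlled, so against documented 12-week control the written rule can only raise DCR. The first five rows give the same result under the alternative DCR.

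One further case is conditional. With new therapy on day 50 and PD on day 80, the subject is controlled only if the BOR restriction carries over to DCR: "BOR will be evaluated over all on-study time-point assessments recorded before start of a new anti-cancer therapy". SAP 7.7.4 does not say whether it does.

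**Comparison with other endpoints.** The day-60 death is a PFS event under SAP 7.7.9 at 60 / 7 = 8.6 weeks, short of 12, yet a DCR success. DOR in SAP 7.7.3 has rules for death, new therapy and missed scans. ORR in SAP 7.7.1 keeps subjects without any follow-up assessment in the denominator as non-responders. TCR counts the first five histories by design, so for these subjects DCR and TCR coincide.

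**Size.** One subject at the planned N of 150 is 1 / 150 = 0.67 points. The DCR denominator is the ITT EAS, whose size is not given; at an assumed 140 or 160 the figure is 0.71 or 0.63. The number affected cannot be derived. Purely as assumptions, 5, 10 or 15 of 150 would add 3.3, 6.7 or 10.0 points.

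**Planned sensitivity analyses.** The alternative DCR has the same gap. The 12-month subset in SAP 7.7.7 selects on time from first dose to data cutoff, not on scans done. The per-protocol set may drop some subjects for important deviations, but a death is not a deviation.

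**The case against.** The strongest reply is that SAP 7.7.4 should not be read alone. SAP 3.5 states the 12-week requirement, 7.7.4 ties its cutoff to 12 weeks, SAP 4.1 declares no change to DCR, and TCR exists for SD seen only to week 6. A subject dead on day 60 does not have 12 weeks of SD under SAP 3.5. This stands in part: the intended reading is visible, so the fault is a conflict between the headline definition and the derivation. It does not remove the fault, because the derivation is the operative text and SAP 3.5 does not say how to classify a subject who is alive but unscanned at week 12.

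It is also fair that DCR is descriptive, that PFS counts the deaths, and that time-point responses are listed, so affected subjects can be found. Eligibility (life expectancy of at least 3 months, ECOG 0 or 1) limits their number, and the imaging rules conflict, so missing week-12 scans should not be presumed routine.

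A reader might infer that the gap between the week-6 scan and day 81 measures the defect. It does not: a fully compliant subject scanned on days 42 and 84 has the same gap. A reader might also infer that the no-PD wording departs from the protocol for everyone; for subjects observed to week 12 it does not.

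Finally, a hard day-81 cutoff for the required scan would discard a week-12 scan done a few days early, contrary to SAP 5.5, which analyses out-of-window data at the intended visit. That objection is right, and the fix allows for it.

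**Conclusion.** The point holds as a conflict within the plan. As written, both DCR versions credit SD subjects whose disease was not shown to be controlled to week 12, including some who died before it, and neither SAP 5.10 with Section 7.7 nor the planned sensitivity analyses corrects this. The effect is upward only, at 0.67 points per subject if N is 150; no total can be claimed. This rests on taking SD in 7.7.4 to be SD as defined in 7.7.1, and on measuring against documented control. A truly stable but unscanned subject would be credited correctly, though without evidence.

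Nothing here supports a wider inference about the trial's main result. ORR does not use this derivation, and SAP 7.1 plans no formal hypothesis testing. It is worth correcting because the correction is small and restores the distinction between DCR and TCR.

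**What to change.** In the 81-day limb of both DCR definitions in SAP 7.7.4, for IERC and investigator assessments:

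- Count an SD subject as controlled only if there is an evaluable assessment at the week-12 visit (including an out-of-window scan assigned to that visit under SAP 5.5) or later, with no PD within 81 days and no death or new anticancer therapy before that assessment.
- Keep all other SD subjects in the denominator as not controlled, and report how many there are.
- State whether day 81 uses the +1 day count of SAP 7.2. With it, the on-schedule week-12 window becomes days 82 to 88 instead of 81 to 87, which decides whether PD at the very start of that window falls within 81 days.

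Leave the limb for durable SD following PD, and the present classification of PD first seen at the week-12 scan, unchanged.

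The cost is one or two sentences and a small programming change. The reported DCR may be slightly lower, and truly stable subjects without a week-12 or later scan will count as not controlled.

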7.7.5. Tumor Control Rate

Tumor control rate (TCR) is defined as proportion of subjects who have BOR of either SD (as defined previously) or a confirmed objective response (CR or PR).

TCR and number of subjects with tumor control will be tabulated using IERC and investigator assessments.

7.7.6. Efficacy Analysis Plots

The following plots will be provided for Safety and Efficacy Analysis Set, respectively:

- Waterfall plots of the best percentage change in tumor size (i.e., maximum tumor reduction, or minimum increase in the absence of any reduction) (Gillespie *et al* 2012).
- Swim lane plot for responders in ITT EAS and ITT PLT sets.

7.7.7. Sensitivity Analyses of Efficacy

The analysis of efficacy per IERC in ITT EAS and ITT PLT, including summary of BOR, ORR, DCR, TCR, DOE will be performed:

- Using alternative definition of BOR, ORR, DOE, and PFS based on evaluation per IERC
- Using a subset of patients with minimum expected follow up (i.e., time from first dose until data cutoff) of at least 12 months (analysis of BOR, ORR, DCR, and TCR only)

Sensitivity analysis will be also performed by using PP EAS.

7.7.8. Subgroup Analyses of Efficacy

Summaries of BOR, ORR, DOR, DCR, and TCR and the waterfall plot, for IERC assessment will be reported in the following subgroups:

- by PD-L1 status (positive, negative, unknown)
- by histology (squamous, adenocarcinoma, other)
- by prior use of bevacizumab (yes vs no)
- by region/country (regions: USA, EU, other)
- by age groups (age < 55 vs \geq 55, age < 65 vs age \geq 65, age < 75 vs age \geq 75)
- by race group including at least 5 subjects and grouping together all categories with < 5 subjects as “Other” (since race was not reported for patients treated in France due to local regulations these patients will be summarized as “Not reported (France)” category).
- by tumor burden (sum of baseline target lesions by investigator assessment) \leq 50 mm vs > 50 mm

Sensitivity analysis by PD-L1 status in ITT AES and ITT PLT analysis sets will be performed both for primary and alternative definitions of BOR, ORR, DOR, and PFS.

These subgroup evaluations will apply to primary analyses in ITT EAS and to secondary analysis in ITT PLT analysis sets.

7.7.9. Progression-Free Survival

Progression-free survival (PFS) is defined as the interval from the date of first dose of investigational agent until the earliest date of PD, as determined by IERC and investigator assessment of objective radiographic disease assessments per RECIST 1.1, or death due to any cause if occurring sooner than progression.

The primary analysis will be performed ignoring transient PDs, using the same definition of transient PDs as in section 7.7.1. Thus, the terminating event will be a non-transient PD or death, whichever occurs first. Patients who did not experience a non-transient PD or death will be censored on the date of last evaluable tumor assessment or the date of initiation of new anti-cancer therapy (if applicable), whichever comes earlier.

The alternative (sensitivity) analysis will be performed for terminating event of death or first observed time-point PD, whichever occurs first. Censoring will be on the date of last evaluable tumor assessment, the date of the last evaluable assessment before two or more consecutive missed imaging visits, or the date of initiation of new anti-cancer therapy (if applicable), whichever occurs first.

For ITT EAS and ITT PLT analysis sets, PFS will be summarized using PD assessments by IERC and by Investigator.

PFS will be reported in months. Median PFS will be provided (estimated using K-M estimate, with 95% CI) and Kaplan-Meier curves of PFS will be plotted using ITT EAS and ITT PLT.

Listing will be provided for Safety Analysis Set.

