7.7.3. Duration of Response

Duration of response (DOR) will be analyzed only for subjects who responded to the study treatment. DOR is defined as the time from first observation of CR or PR which was subsequently confirmed until the first time of disease progression or death by any cause within 12 weeks of last tumor assessment. All assessments performed before initiation of a new anti-cancer therapy will be considered for evaluation of DOR. Similar to evaluation of BOR, in the primary analysis any transient time-point PD(s) will be disregarded for determination of DOR when followed by confirmed objective response or durable stable disease, as defined in section 7.1.1. In the alternative (sensitivity) analysis, DOR will be counted using the date of first observed PD, whether transient or not.

The starting event for DOR will be the date of first objective response. The terminating event will be date of PD or death within 12 weeks of last tumor assessment, whichever occurs first. The censoring event will be the earliest of the dates of last evaluable assessment, last evaluable assessment performed before initiation of new anti-cancer therapy (if applicable), or before 2 or more missed imaging assessments (i.e., no assessment within 90 days) followed by PD or death.

DOE will be reported in months and summarized by quartiles estimated from Kaplan-Meier curve, as well as Kaplan-Meier estimates at 6, 9, 12, 18 months. Number and percent of censored and non-censored observations and a plot Kaplan-Meier curve will be provided.

In addition, duration of observation of DOE (whether censored or not) will be summarized as “Observed DOE”, including the shortest and longest observation will be provided with censoring indicator.

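### SAP 7.7.9: the primary PFS analysis censors at new anti-cancer therapy only subjects who never have an event, so time after a switch counts only when it ends in progression or death

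*SAP*

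**What the plan says.** SAP 7.7.9 governs the primary analysis of PFS. Three parts of it matter.

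- **Event.** "Thus, the terminating event will be a non-transient PD or death, whichever occurs first". Deaths are included by the phrase "or death due to any cause if occurring sooner than progression". Neither statement requires the event to come before new anti-cancer therapy.
- **Censoring.** "Patients who did not experience a non-transient PD or death will be censored on the date of last evaluable tumor assessment". The sentence then gives a second possible date, the start of another cancer treatment, and takes whichever of the two is first. The opening words confine the whole sentence to subjects without an event.
- **Alternative (sensitivity) analysis.** It also lists the new-therapy date as a censoring date, with the earliest date applying, but it is not confined to event-free subjects.

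The neighbouring endpoints treat the switch differently. For best response, SAP 7.7.1 says that "BOR will be evaluated over all on-study time-point assessments recorded before start of a new anti-cancer therapy". SAP 7.7.3 likewise restricts DOR to assessments made before new therapy and names the last of these as a censoring date.

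The endpoint definition of PFS in SAP 3.5, and in the protocol synopsis and section 2.1.2, counts a death only if it falls no more than 12 weeks past the latest tumor assessment. SAP 7.7.9 has no such limit.

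**The concern.** Take two subjects who start another drug on the same day without RECIST progression. One dies later and is an event on the date of death. The other is still alive at cutoff and is censored at or before the switch. Whether each is in the risk set after the switch is decided by what happens afterwards. Kaplan-Meier needs the risk set at any time to be fixed by what is known up to that time.

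The resulting curve answers neither of the usual questions. It is not PFS on balstilimab, which would censor every switcher. It is not PFS regardless of later therapy, which would follow every switcher. More subjects would not remove the discrepancy.

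The plan provides for such switchers:

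- Protocol 4.4.1 withdraws subjects for clinical progression without radiologic progression, and lists starting new antineoplastic therapy among its signs.
- Protocol 6.3.4.2 then follows them for survival by telephone every 2 months, up to 12 months after the last dose, so their deaths are recorded.
- PFS is also reported by IERC. A subject who switches after investigator PD that the IERC has not confirmed is a further case.

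At stake are the PFS curve, and to a lesser degree its median, in both ITT EAS and ITT PLT, and agreement between PFS and DOR in the same responder.

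**Working it through.** The documents state no PFS rate, event count or switch rate, so there is no PFS figure to reproduce. All inputs below are assumptions.

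**1. Ten-subject example.** PD at months 2, 3, 4 and 6 (four subjects). Two subjects are event-free and censored at month 12. Four switch at month 3 with last scan at 2.8; two of them die at months 7 and 9, and two are alive at 14. The Kaplan-Meier estimate is the product of (1 − 1/number at risk) over event times.

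| Rule | 9-month PFS | Median (first time the curve is at or below 50%) |
|---|---|---|
| As written (survivors out at 2.8, deaths counted) | 9/10 × 6/7 × 5/6 × 4/5 × 3/4 × 2/3 = 25.7% | 7.0 |
| All four switchers censored at 2.8 | 9/10 × 4/5 × 3/4 × 2/3 = 36.0% | 6.0 |
| All four followed | 9/10 × 8/9 × 7/8 × 6/7 × 5/6 × 4/5 = 40.0% | 7.0 |

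At 9 months the written rule lies below both consistent rules, so it is not a compromise between them.

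**2. Same example under the 12-week limit of SAP 3.5.** The first death is (7 − 2.8) × 30.4375 = 128 days after the last scan, more than 84. Neither death would count, and the as-written result becomes 36.0%, equal to consistent censoring. If instead the two deaths fall at months 4.5 and 5 (52 and 67 days after the last scan), both count. The at-risk numbers run 10, 7, 6, 5, 4, 3 as before, and 9-month PFS is again 25.7%, against 36.0% and 40.0%. The limit narrows the problem but does not remove it.

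**3. Simulation, 400,000 subjects per scenario.** Time to PD is exponential with median 3 or 5 months. The switch rate is the PD rate × s/(1 − s), which makes the chance of switching before PD equal to s = 5, 10, 20 or 30%. Median survival after the switch is 4 or 8 months. Scans are every 6 weeks and stop at the switch; deaths are recorded for 12 months after it; follow-up is uniform over 6–24 months; no 12-week limit is applied. Over the 2 × 4 × 2 = 16 scenarios:

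- 2.7–25.3% of PFS events fall after the switch.
- 12-month PFS as written is 0.1–5.8 points below consistent censoring and 0.4–10.3 points below following everyone. Smallest gap to consistent censoring: 7.6% against 7.7% (PD median 3, s = 5%, post-switch survival 8). Largest: 14.6% against 20.4% (PD median 5, s = 30%, post-switch survival 4).
- The median differs in one scenario only (3.77 against 4.14 months).
- At 6 months the direction is not fixed. With PD median 3, s = 30% and post-switch survival 8, the written rule gives 27.6% against 25.8%.

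**4. Effect of the 12-week limit in two other simulations.**

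- Switching caused by clinical progression in 30% of subjects: without the limit the medians are 4.7–5.0 months as written against 4.1. With it, both are 4.1 and the 12-month gap is about 1.3–1.8 points.
- Independent switch and event times with medians 12 and 6 months, so that (1/12)/(1/12 + 1/6) = one third would switch first, and post-switch events at the full PFS hazard: with a 12-week window from the switch, 12-month PFS is still 20.9% against 25.0%, and the median 5.4 against 6.0.

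**The case against.** **Stakes.** PFS is secondary and SAP 7.1 plans no formal hypothesis test. SAP 7.7.9 lists only the median with its interval and the curve; a 12-month PFS estimate is not a planned statistic. This stands and limits the importance of the point, though the tail of a plotted curve is read.

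**The death limit.** Under SAP 3.5 a subject who switches at month 4 with no later scan and dies at month 10 is about 26 weeks past the last scan and is not an event. A reader might infer that deaths many months after a switch certainly enter PFS. The documents do not settle that, because 7.7.9 and 3.5 conflict. Early post-switch deaths would still be treated unequally.

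**The alternative analysis.** It can be read as censoring every switcher, so it is wrong to say that the reader has no recourse. But it also changes the transient-PD and missed-visit rules, so a difference between the two analyses could not be attributed to the switch.

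**Scans after a switch.** The synopsis stops scans at a new line of therapy, so post-switch events would be mostly deaths. Table 13, footnote 7, continues imaging after a toxicity stop until central progression, so some PDs could be recorded.

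**Bias of the remedy.** Censoring at a switch prompted by clinical progression is itself informative. In the 30% clinical-progression simulation, scanning everyone to RECIST PD would give 12-month PFS of about 8%. Consistent censoring gives about 15.5% and the written rule 12–13%, which is nearer. This stands and is why a second analysis is needed.

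**Conclusion.** The rule is wrong as written: in the primary PFS analysis, time after a switch enters only when it ends in an event. No other section corrects this, and it is inconsistent with BOR and DOR.

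The effect falls mainly on the tail of the curve, with little change in the median under most assumptions. It depends on the share of subjects who switch before PD, which the documents do not give. At 5% switching, the 12-month gap to consistent censoring is 0.1–0.9 points. If the 12-week limit governs, the effect is generally smaller, and was small where post-switch events were deaths after clinical progression. It was not small when a third switched and kept the full PFS hazard.

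A reader might infer that the reported median will be seriously distorted, or always in one direction. The documents support neither: no switch rate is given, and the sign changed with the assumptions. Nor do they support any effect on ORR or DOR, which have their own rules.

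**What to change.** In SAP 7.7.9, replace the primary censoring sentence with one rule for all subjects, for example: *Subjects who start new anti-cancer therapy before a non-transient PD or death are censored at the last evaluable assessment on or before that start, whether or not PD or death follows.* This aligns PFS with the treatment of the switch in BOR and DOR. It does not copy the whole DOR rule, which also limits deaths to 12 weeks and handles missed assessments.

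Add a sensitivity analysis that counts every PD and death and censors nobody at new therapy. It should otherwise keep the primary rules, so that it isolates the effect of the switch.

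In the same edit, decide whether a PFS death is any death, as in 7.7.9, or only one inside the 12-week window, as in SAP 3.5 and the protocol, and use that definition throughout.

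Cost: a few sentences and one extra run, on data already collected (protocol 6.4.1.9.1 records new therapy). Post-switch deaths no longer count in the primary PFS analysis, so the estimate is slightly less precise. Some informative censoring remains, and the sensitivity analysis would show how much it matters.
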